4.8.9. Concomitant Procedures

Pacemakers and other therapies of interest will be identified by a Sponsor's representative and assigned to categories (PCI, CBAG, ICD, and CRT). These prior procedures will be summarized together with other baseline characteristics.

Prior and concomitant procedures collected in the eCRF will be included in a by-subject data listing. The listing will identify which procedures are prior and which are concomitant.

4.8.10. Quality of Life

Quality of life will be assessed using the Kansas City Cardiomyopathy Questionnaire-12 (KCCQ-12), the European QoL-5 Dimensions (EQ-5D) questionnaire and the Visual analogue scale for Health State, for the FAS and as a sensitivity analysis for the PP set.

The KCCQ-12 is a health-related quality of life questionnaire for heart failure. It is a 12-item questionnaire that quantifies physical function, symptoms (frequency, severity, and recent change), social function, self-efficacy and knowledge, and QoL. KCCQ-12 is assessed at Day 0 (V2), at Week 2 and Week 4, Week 6 (V3), Week 12 (V4), Week 24 (V5), Week 36 (telephone contact 3), and Week 52 (V6). The KCCQ-12 questionnaire is completed before any trial related procedure performed for the visit concerned. For the telephone contacts, subjects complete the self-administered KCCQ-12 questionnaire at home on the same day as the telephone contact. For each time point, an overall score will be calculated from the scores of the different domains. The UK scoring method will be used as described in Appendix V. The overall summary score and the clinical summary score will be summarised at each visit.

The EQ-5D is a quality of life questionnaire including 5 items/dimensions (i.e., mobility, self-care, usual activities, pain/discomfort, and anxiety/depression), which will be coded from 1 (best state) to 5 (worst state), and a visual analogue scale (VAS; vertical, graduated [0-100 points] 20-cm "thermometer," with 100 at the top representing "best imaginable health state" and 0 at the bottom representing "worst imaginable health state"). The EQ-5D is assessed at Day 0 (V2), Week 6 (V3), Week 24 (V5), and Week 52 (V6). An index value will be calculated from these results at each visit (see Appendix VI). For each dimension, the number and percentage of subjects reporting each level will be presented. The VAS result and the change from baseline in VAS will be described as continuous variables at each visit.

Additionally, for each questionnaire, the actual values and change from baseline in overall summary score, clinical summary score and physical limitation score (not part of the main set of outputs) will be descriptively summarized at each visit. Treatment difference in KCCQ-12 scores (one model for each score) at Week 2, Week 4, Week 6, Week 12, Week 24, Week 36, and Week 52 will be analysed by comparing the model-adjusted means of the respective visits based on a repeated-measures model including terms for treatment, baseline, time, and treatment-by-time interaction with an unstructured covariance matrix to model the within-subject variability. Treatment difference in EQ-5D index score will be analysed in the same manner for the data collected at Week 6, Week 24, and Week 52.

SAS code to be used:

```
PROC MIXED DATA=dataset order = internal;  
CLASS usubjid time treatment sex hf_aetio hf_duration country;  
MODEL change=base treatment time treatment*time sex age hf_aetio hf_duration country  
/ddfm=kenwardroger;  
REPEATED time / subject=usubjid type=un;  
LSMEANS treatment *time / pdiff cl at means;  
RUN;
```

Number and percentage of subjects with improvement of ≥ 5 points, improvement of ≥ 8 points and deterioration of ≥ 5 points will be presented for KCCQ-12 overall summary score, clinical summary score and physical limitation score at Week 2, Week 4, Week 6, Week 12, Week 24, Week 36 and Week 52. Odds ratio for FCM vs placebo will be presented as well. This analysis will not be part of the main set of outputs.

Results from quality of life questionnaires will be reported in data listings, with details by question and by visit.

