9.2.3.10 Health-related Quality of Life

KCCQ-12 – Kansas City Cardiomyopathy Questionnaire

Health-related quality of life (HRQoL) will be assessed using the validated KCCQ-12. The KCCQ-12 is a self-administered, disease-specific instrument for measuring HRQoL in subjects with HF regardless of aetiology. It is a 12-item questionnaire that quantifies physical function, symptoms (frequency, severity and recent change), social function, self-efficacy and knowledge, and QoL [35]. Validated official translations in the local language versions will be used. The subject should complete the paper-based KCCQ-12 before any other assessment or procedure for the visit concerned is performed. The subject should complete the questionnaires in a quiet environment.

Source data verification will be performed for paper-based questionnaires. Once completed by the subjects, data will be entered into the eCRF by site staff. The manual of operations will detail how the data flow will be handled.

EQ-5D – European Quality of Life – 5 Dimensions

The EQ-5D questionnaire is a brief, utility-based generic HRQoL instrument. It consists of a health descriptive system and a visual analogue scale (VAS) for respondents to self-classify and rate their health status on the day of administration of the instrument. [36] The descriptive system has 5 items/dimensions (i.e. mobility, self-care, usual activities, pain/discomfort and anxiety/depression). The VAS is a vertical, graduated (0-100 points) 20 cm “thermometer”, with 100 at the top representing “best imaginable health state” and 0 at the bottom representing “worst imaginable health state”. The VAS records the respondent’s self-rated health on a 20 cm vertical, VAS with endpoints labelled “the best health you can imagine” and “the worst health you can imagine”. This information can be used as a quantitative measure of health as judged by the individual respondents. Validated official translations in the local language versions will be used. The subject should complete the paper-based EQ-5D after the KCCQ-12 but before any other assessment or procedure for the visit concerned is performed. The subject should complete the questionnaires in a quiet environment.

Source data verification will be performed for paper-based questionnaires. Once completed by the subjects, data will be entered into the eCRF by site staff. The manual of operations will detail how the data flow will be handled.

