12.10.3 Quality of Life

Quality of Life will be assessed using the KCCQ-12 and EQ-5D. The analysis of treatment difference on the KCCQ-12 score at Week 2, Week 4, Week 6, Week 12, Week 24, Week 36 and Week 52 will be done by comparing the model adjusted means of the corresponding visit based on a model for repeated-measures including terms for treatment, baseline, time and treatment-by-time with an unstructured covariance matrix to model the within-patient variability. The analysis of treatment difference on the EQ-5D score will be done in the same manner for the data collected at Week 6, Week 24 and Week 52. The SAP will detail the analysis to be performed.

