2.5.3. Other Endpoints

- The composite of recurrent HF hospitalisations and CV death up to 30 days after randomisation
- The composite of recurrent CV hospitalisations and CV death up to 30 days after randomisation
- The composite of HF hospitalisations or CV death analysed as time to first event up to 30 days after randomisation.
- The composite of CV hospitalisations or CV death analysed as time to first event up to 30 days after randomisation.
- HF hospitalisations up to 30 days after randomisation (analysed as a recurrent event).
- HF hospitalisations up to 30 days after randomisation (analysed as time to first event).
- HF hospitalisations up to 52 weeks after randomisation (analysed as time to first event).
- CV hospitalisations up to 30 days after randomisation (analysed as a recurrent event and time to first event).
- CV hospitalisations up to 52 weeks after randomisation (analysed as a recurrent event and time to first event).
- The composite of CV hospitalisations or CV death analysed as time to first event up to 30 days after randomisation.
- The composite of CV hospitalisations or CV death analysed as time to first event up to 52 after randomisation.
- CV mortality analysed as time to first event up to 30 days after randomisation.
- All-cause mortality analysed as time to first event up to 30 days after randomisation.
- All-cause mortality analysed as time to first event up to 52 weeks after randomisation.
- Proportion of subjects with an event (HF hospitalisations, CV hospitalisations, CV mortality; composite and individual categories).
- Change from baseline in NYHA functional class as assessed at 6, 12, 24, and 52 weeks after randomisation.
- Change from baseline in the Kansas City Cardiomyopathy Questionnaire-12 (KCCQ-12) Overall Summary Score, Clinical Summary Score and Physical Summary Score to weeks 2, 4, 6, 12, 24, 36 and 52 after randomisation.

- Percentage of subjects with improvement of ≥ 5 or ≥ 8 points and percentage of subjects with ≥ 5 points deterioration from baseline in KCCQ-12 Overall Summary Score, Clinical Summary Score and Physical Summary Score to weeks 2, 4, 6, 12, 24, 36 and 52 after randomisation.
- Change from baseline in the European Quality of Life – 5 Dimensions questionnaire indexed value and VAS at weeks 6, 24 and 52 after randomisation.
- Days lost due to HF hospitalisations or CV death up to 30 days after randomisation.

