4.6.2. Secondary and Other Endpoints

The secondary and other endpoints listed below will evaluate the effect of IV FCM relative to placebo. These will be analysed on the FAS and as a sensitivity analysis on the PP set, using adjudicated events based on the final decision of the CEC.

Secondary endpoints:

- The composite of recurrent CV hospitalisations and CV death up to 52 weeks after randomisation.
- HF hospitalisations up to 52 weeks after randomisation (analysed as a recurrent event).
- CV mortality analysed as time to first event up to 52 weeks after randomisation.
- The composite of HF hospitalisations or CV death analysed as time to first event up to 52 weeks after randomisation.
- Days lost due to HF hospitalisations or CV death up to 52 weeks after randomisation.

Hochberg's procedure will be used to control the overall Type I error for the evaluation of the secondary endpoints on FAS at the FWER of 5% two-sided. All secondary endpoints will be analysed as described further in this section, p-values will be sorted from the smallest to the largest and compared with Hochberg's critical values (see Table 5). The highest p-value with lower value than the Hochberg's critical value will be chosen. This p-value and all lower p-values will be considered statistically significant at overall level 5% two-sided.

Table 5 Hochberg's Critical Values

Ordered p-values	Hochberg's critical values
p-value ₁	0.05/5 = 0.01
p-value ₂	0.05/4 = 0.0125
p-value ₃	0.05/3 = 0.0166
p-value ₄	0.05/2 = 0.025
p-value ₅	0.05/1 = 0.05

Other endpoints:

- The composite of recurrent HF hospitalisations and CV death up to 30 days after randomisation.
- The composite of recurrent CV hospitalisations and CV death up to 30 days after randomisation.
- The composite of HF hospitalisations or CV death analysed as time to first event up to 30 days after randomisation.
- The composite of CV hospitalisations or CV death analysed as time to first event up to 30 days after randomisation.
- HF hospitalisations up to 30 days after randomisation (analysed as a recurrent event).
- HF hospitalisations up to 30 days after randomisation (analysed as time to first event).
- HF hospitalisations up to 52 weeks after randomisation (analysed as time to first event).
- CV hospitalisations up to 30 days after randomisation (analysed as a recurrent event and time to first event).
- CV hospitalisations up to 52 weeks after randomisation (analysed as a recurrent event and time to first event).

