		14.5.1.4.1 EQ-5D-5L: Individual Categories – Full Analysis Set
		14.5.1.4.2 EQ-5D-5L: Individual Categories – Per Protocol Set
		14.5.1.5.1 EQ-5D-5L VAS and Index Score: Actual Values and Changes from Baseline – Full Analysis Set
		14.5.1.5.2 EQ-5D-5L VAS and Index Score: Actual Values and Changes from Baseline – Per Protocol Set
		14.5.1.6.1 EQ-5D-5L Repeated-Measures Model for Analysis of Treatment Difference (Index Score)– Full Analysis Set
		14.5.1.6.2 EQ-5D-5L Repeated-Measures Model for Analysis of Treatment Difference (Index Score) – Per Protocol Set

Type*	Section	Title
L	16.2 Individual Subject Data Listing	16.2.1.1 Subject Disposition and Study Termination Information – All Screened Population

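### EQ-5D VAS is listed as an endpoint beside the index value, but the SAP models the treatment difference for the index only and plans no baseline-adjusted between-arm estimate for VAS

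*SAP*

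**What the plan says.** SAP section 2.5.3 includes among the other endpoints the change from baseline in the EQ-5D "questionnaire indexed value and VAS at weeks 6, 24 and 52 after randomisation". The index and the VAS appear in the same item with no difference in standing.

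SAP section 4.6.2 opens with "The secondary and other endpoints listed below will evaluate the effect of IV FCM relative to placebo". Its own list names change in the EQ-5D questionnaire and refers the reader to section 4.8.10 for the method.

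SAP section 4.8.10 treats the two parts of the instrument differently. For the VAS: "The VAS result and the change from baseline in VAS will be described as continuous variables at each visit". For the index: "Treatment difference in EQ-5D index score will be analysed in the same manner", that is, by the repeated-measures model set out for KCCQ-12, at Weeks 6, 24 and 52.

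The output list in SAP section 7.1 follows the same split. Tables 14.5.1.5.1 and 14.5.1.5.2 are titled "EQ-5D-5L VAS and Index Score: Actual Values and Changes from Baseline" (FAS and PP). The EQ-5D model tables, 14.5.1.6.1 and 14.5.1.6.2, are labelled for the index score only.

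Protocol section 12.10.3 is less specific: "The analysis of treatment difference on the EQ-5D score will be done in the same manner". It leaves the detail to the SAP.

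**The concern.** Two parts of the SAP do not meet. One names VAS as an endpoint in a group whose stated purpose is comparison with placebo. The other plans for VAS only summaries by arm and visit, with no treatment contrast. Quality of life relative to placebo is also a secondary objective (SAP section 1.2.1).

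Three things are at stake, all modest.

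- **Pre-specification.** If a modelled VAS difference is wanted after unblinding, it will be post hoc, although the model is already written for the index.
- **Quality of the substitute.** Visit summaries use whoever has a value at that visit, without baseline adjustment. Protocol section 12.2 anticipates CV death in 12% of subjects, and the minimum data set for a remote Week 52 visit (protocol section 4.1.3) does not include the questionnaires. The repeated-measures model would use all available post-baseline visits and adjust for baseline and covariates. It would not solve missingness due to death.
- **Information.** VAS does not duplicate the index. SAP Appendix VI applies one UK value set to a trial with fifteen countries in SAP Table 4. VAS is the respondent's own rating and needs no value set.

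**Working it through.** The plan states no figure on this point, so there is none to reproduce. The check has two parts: the text, then the size of the precision loss.

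**Text.** Every mention of EQ-5D and VAS in both documents was compared.

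| Question | Index value | VAS |
|---|---|---|
| Named endpoint (SAP 2.5.3) | Yes, Weeks 6, 24, 52 | Yes, Weeks 6, 24, 52 |
| Descriptive values and changes (SAP 4.8.10; Tables 14.5.1.5.1-2) | Yes | Yes |
| Repeated-measures treatment difference (SAP 4.8.10) | Yes | No |
| Model output table (14.5.1.6.1-2) | Yes | No |

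The methods text and the output list agree, so this is not a slip in one sentence. No between-arm VAS estimate, interval or test is planned.

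**What a reader could still derive.** SAP section 4.2.1 requires the mean and SD for continuous variables, and Tables 14.5.1.5.1-2 give both actual values and changes. If the number observed is also shown, a crude difference with a 95% CI can be formed from either.

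**Precision of that crude difference.** Assumptions: one visit at a time, common SD σ at baseline and follow-up, equal SDs in the arms, correlation ρ between baseline and follow-up, and a sample large enough to ignore the degree of freedom spent on the covariate. The documents give no ρ; 0.2 to 0.5 is assumed.

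The variance per subject is:

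- follow-up value: σ²
- raw change: 2σ²(1 − ρ)
- baseline-adjusted: σ²(1 − ρ²)

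The SE ratios to the baseline-adjusted analysis are:

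- follow-up means: 1/√(1 − ρ²)
- raw changes: √[2(1 − ρ)/(1 − ρ²)] = √[2/(1 + ρ)]

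| ρ | Follow-up means | Raw changes |
|---|---|---|
| 0.2 | 1/√0.96 = 1.02 | √(2/1.2) = 1.29 |
| 0.3 | 1/√0.91 = 1.05 | √(2/1.3) = 1.24 |
| 0.4 | 1/√0.84 = 1.09 | √(2/1.4) = 1.20 |
| 0.5 | 1/√0.75 = 1.15 | √(2/1.5) = 1.15 |

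The two meet where 2(1 − ρ) = 1, that is ρ = 0.5. Above that, raw change is the better of the two (at ρ = 0.7, √(2/1.7) = 1.08). Under these assumptions the better simple comparison therefore never costs more than about 15%, but which one is better depends on a correlation that is not known in advance.

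**The case against.** The strongest case is that descriptive reporting of VAS is a deliberate choice. VAS is named only in SAP section 2.5.3, which has no sentence about evaluating an effect. That sentence is in section 4.6.2, whose list gives the EQ-5D questionnaire without mentioning VAS. The named quantity, change from baseline by visit, will be tabulated. Modelled differences for the KCCQ-12 summary scores and the EQ-5D index already serve the quality-of-life objective.

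Part of this stands. The agreement between methods and outputs does suggest intent, and the consequence is small. It does not remove the mismatch: sections 2.5.3 and 4.6.2 list the same group of endpoints, and nothing in the SAP says that VAS is exempt from the comparative purpose.

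Three stronger readings are tempting, and the documents do not support them.

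- *The trial will yield no VAS comparison beyond eyeballing raw changes.* Means and SDs of both values and changes are planned by arm, so a crude difference and interval can be derived.
- *The SAP contradicts the protocol and fails to record it.* Protocol section 9.2.3.10 does describe the EQ-5D as including the VAS ("It consists of a health descriptive system and a visual analogue scale (VAS) for respondents to self-classify and rate their health status"), and SAP section 5 records only the change to the age covariate. But the protocol's endpoint does not name VAS, its analysis text speaks of an EQ-5D score in the singular, and it defers to the SAP. Taking that score to be the index is a permissible specification.
- *Up to 29% of precision is lost.* That figure belongs to raw changes at ρ = 0.2; comparing follow-up means at the same ρ costs 2%. Either way it describes a calculation that a reader might make, not an analysis the trial will run.

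**Conclusion.** The point holds in a limited form. The SAP lists VAS change at three visits as an other endpoint and gives those endpoints a comparative purpose, but plans no pre-specified, baseline-adjusted VAS difference or confidence interval. This finding rests on the text alone and needs no assumption.

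The size of the loss does rest on assumptions. With equal SDs and ρ between 0.2 and 0.5, a crude substitute has a standard error about 2-15% larger (follow-up means) or 15-29% larger (raw changes) than a baseline-adjusted analysis.

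VAS is outside the Hochberg family. The sample size and the primary and secondary conclusions are untouched. Severity is low, but the remedy is a method the SAP already applies to the companion score, with no new data, so it is worth making before unblinding.

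**What to change.** In SAP section 4.8.10, widen the sentence on the EQ-5D index so that it covers both scores, for example: *Treatment differences in the EQ-5D index score and in the EQ-5D VAS will each be estimated with this repeated-measures model at Weeks 6, 24 and 52.* Add the VAS model results to Tables 14.5.1.6.1 (FAS) and 14.5.1.6.2 (PP). The PROC MIXED code in that section can be reused with change in VAS as the response and the Day 0 VAS as the baseline term.

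The cost is one further model, run in each analysis set, and the added table output. Because the code compares arms at each visit, it adds three nominal p-values per analysis set, six over FAS and PP (3 × 2), none of them controlled for multiplicity. They should be labelled nominal, with the estimate and interval given first.

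If descriptive reporting is what the sponsor intends, the minimum is to say so for VAS in section 2.5.3, so that the endpoint list and section 4.8.10 agree. That removes the inconsistency but leaves VAS without an adjusted comparison.

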9.2.1.2 Baseline Visit, Randomisation and Administration of the First Dose of Study Treatment

The baseline visit will be performed in-hospital for subjects from whom the screening visit blood test results confirm ID and Hb ≥ 8 g/dL* and ≤ 15 g/dL. For females of childbearing potential, the serum pregnancy test must be negative.

*Following section in italics is applicable for The Netherlands, Spain and Singapore only (NL, ES and SG only):

The lower threshold of Hb values is set to 10 g/dL.

The following assessments will be performed for the baseline visit:

- Completion of the self-administered KCCQ-12 and European quality of life – 5 dimensions questionnaire (EQ-5D) (see Section 9.2.3.10)
- Physical examination (see Section 9.2.3.2)
- Recording of body height and weight (see Section 9.2.3.3)
- Recording of vital signs (i.e. seated blood pressure, pulse rate, and rhythm (see Section 9.2.3.3)
- 12-lead electrocardiogram (ECG) (see Section 9.2.3.7)
- Recording of the appropriate medical history (see Section 9.2.3.1)
- Assessment of symptoms and signs related to HF (see Section 9.2.3.5)
- Assessment of NYHA class (see Section 9.2.3.6)
- Documentation of prior and current concomitant treatments (see Section 9.2.3.8)
- Check for the occurrence of AEs since the signing of informed consent (see Section 10)
- Final review of inclusion/exclusion criteria and confirmation of eligibility (see Sections 5.2 and 5.3)
- Randomisation (see Section 9.2.3.12)

- Blood sampling for biomarkers in a subset of subjects (see Section [9.2.3.11](#))
- Prepare and administer first dose of study treatment (see Section [9.2.3.13](#))
- Hand-out subject identification card at hospital discharge
- Provision of the self-administered questionnaire (KCCQ-12) for completion at Telephone Call 1 (Week 2) and Telephone Call 2 (Week 4)

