2. STUDY DESIGN

2.1. Synopsis of Study Design

This is a phase 4, randomised, double-blind, placebo-controlled trial. The 52-week observation period following randomisation is considered appropriate to investigate the primary endpoint of the composite of recurrent HF hospitalisations and CV death. To evaluate the effect of IV FCM in iron deficient subjects with AHF, subjects will be enrolled during a hospital stay (Index hospitalisation) after the acute care treatment of the index event has been stabilised.

All subjects will continue to receive their established standard therapy for HF, and medical emergencies will be treated according to local routine. First study drug will be administered in the hospital prior to discharge for the index hospitalisation. Over the 52 weeks following randomisation, the collected endpoints will focus on important events for this subject population (hospitalisations, mortality and QoL) that directly impact the subjects and the health care system.

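### The KCCQ-12 and EQ-5D repeated-measures model holds the baseline slope equal at all visits; a visit-specific slope costs almost nothing and would recover some precision, mainly at Week 52, if the slope changes over follow-up

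*SAP*

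**What the plan says.** SAP 4.8.10 describes a "repeated-measures model including terms for treatment, baseline, time, and treatment-by-time interaction with an unstructured covariance matrix", and Protocol 12.10.3 describes "a model for repeated-measures including terms for treatment, baseline, time and treatment-by-time with an unstructured covariance matrix". The SAP code agrees with the text: the mean model is "MODEL change=base treatment time treatment*time sex age hf_aetio hf_duration country" and the covariance is set by "REPEATED time / subject=usubjid type=un". Neither text nor code has a baseline-by-time term, and no other section adds one.

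KCCQ-12 differences "at Week 2, Week 4, Week 6, Week 12, Week 24, Week 36, and Week 52 will be analysed", with a separate model for each score. The EQ-5D index is handled "in the same manner for the data collected at Week 6, Week 24, and Week 52".

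On timing, Protocol 9.2.1.2 states "The baseline visit will be performed in-hospital for subjects" whose screening bloods qualify. SAP 2.1 places enrolment "after the acute care treatment of the index event has been stabilised". Protocol 4.1.2 also requires IV drugs for the episode to have been stopped for at least 12 hours before randomisation. The response options in SAP Appendix V show that the KCCQ-12 symptom items refer to the past two weeks.

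Both questionnaires are listed under other endpoints in SAP 2.5.3. They are not among the five secondary endpoints tested by Hochberg's procedure, although quality of life is named in a secondary objective.

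**The concern.** The model lets the visit means, the treatment effect and the whole covariance matrix vary by visit, but not the baseline coefficient. Here there is a specific reason to expect that it might vary. The baseline score is taken in hospital and its recall period can reach into the acute episode, whereas the modelled visits extend to a year later. A score obtained in that setting may predict Week 2 better than Week 52.

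If the true slopes differ, the single fitted slope is a weighted compromise. At visits where it misses, the unexplained part of the baseline relation stays in the residual variance, and the treatment difference at that visit gets a wider interval than necessary. What is at stake is the precision of the visit-specific quality-of-life comparisons, using data that are already collected.

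**Working it through.** **Inputs.** From the documents: the model terms, seven KCCQ-12 visits, three EQ-5D visits and 1:1 allocation. The check uses 500 per arm, the sample-size target before the allowance for loss to follow-up (SAP 4.1). The documents give no SD, baseline-to-visit correlation or power for these scores, so there is no plan figure to reproduce. Correlations, SDs and the between-visit covariance below are assumptions.

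**Formula.** Let B_t be the slope of the score at visit t on baseline. Using change as the response subtracts 1 from every B_t and alters nothing that matters here. With an unstructured residual covariance, W its inverse, and complete data, the common slope is

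b_c = (1′W B) / (1′W 1),

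and relative to a visit-specific slope the variance of the treatment difference at visit t is multiplied by

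1 + (B_t − b_c)² × Var(baseline) / (residual variance at t).

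With equal SDs at baseline and every visit, B_t is the baseline-to-visit correlation r_t, and the last factor is 1/(1 − r_t²).

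**KCCQ-12, Week 52.** Baseline correlation falls linearly in log time. The between-visit correlation is 0.8 minus 0.3 times the log-time distance, scaled so that Week 2 to Week 52 is 1.

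| Correlation, Week 2 to Week 52 | b_c | Variance ratio at Week 52 | Range under other assumed structures |
|---|---|---|---|
| flat at 0.40 | 0.400 | 1 + 0 = 1.000 | 1.000 |
| 0.45 to 0.35 | 0.403 | 1 + 0.053²/0.8775 = 1.003 | 1.003–1.007 |
| 0.6 to 0.4 | 0.521 | 1 + 0.121²/0.84 = 1.017 | about 1.01–1.03 |
| 0.6 to 0.3 | 0.497 | 1 + 0.197²/0.91 = 1.043 | about 1.03–1.07 |
| 0.7 to 0.3 | 0.605 | 1 + 0.305²/0.91 = 1.102 | about 1.09–1.13 |

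The ranges in the last two rows cover most of the structures tried. Some covariance and decay choices go higher, up to 1.15 for 0.6 to 0.3.

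**Interval width.** For 0.6 to 0.3, √1.03 = 1.015 and √1.07 = 1.034, so roughly 2 to 3%. A ratio of 1.043 is equivalent to analysing 1,000/1.043 = 959 subjects instead of 1,000.

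**Week 2.** For 0.6 to 0.3 the ratio is 1 + (0.6 − 0.497)²/0.64 = 1.017. The loss is therefore not confined to the late visits.

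**EQ-5D, Week 52.** With three visits and the same pattern starting at Week 6, 0.6 to 0.3 gives b_c = 0.491 and 1 + 0.191²/0.91 = 1.040.

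**Simulation.** 3,000 trials per setting with 500 per arm, complete data, assumed SD 20 and a true difference of 3 points. Week 52 power, common slope against visit-specific slopes, was 68.9% against 70.4% for 0.6 to 0.3, 64.6% against 70.5% for 0.7 to 0.3, and 74.1% against 74.0% for a flat 0.4. Mean bias at Week 52 was within simulation error of zero in every setting.

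**Changing SDs.** The model constrains the slope, and B_t = r_t × SD_t/SD_baseline. If the correlation falls from 0.6 to 0.4 while the SD rises 1.5-fold, the Week 52 slope is 0.4 × 1.5 = 0.6, the same as at Week 2, and the ratio is 1.000. For 0.6 to 0.3 with the same rise, the Week 52 slope is 0.3 × 1.5 = 0.45 and the ratio is only 1.007 to 1.015.

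**The case against.** The strongest reply is that nothing here is wrong. The model is pre-specified identically in both documents and is valid under randomisation, and the proposed term helps only if slopes differ. The documents contain no figure that shows they do. An in-hospital baseline could predict every later visit equally weakly, in which case the loss is zero; a falling correlation offset by a rising SD gives the same result. Even where there is a loss, it is small, and it falls on endpoints outside the Hochberg family for which the trial was not powered. All of this stands, and it is why the point is an optional refinement and not an error.

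Three stronger readings are tempting, and the documents do not support them.

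- A reader might infer that precision is certainly lost. That needs slopes the documents do not give.
- A reader might infer that the baseline is recorded in the middle of untreated decompensation. Enrolment follows stabilisation; only the two-week recall can reach back into the episode.
- A reader might infer biased treatment differences. With complete data the simulations show none. Dropout was not examined, and no claim is made about it.

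What the reply does not answer is the asymmetry. If slopes are equal, the extra term costs practically nothing; if they differ, it recovers precision from data already in hand. The SAP accepts this reasoning elsewhere: section 5 replaces categorical with continuous age in the adjustments to gain precision.

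**Conclusion.** The point holds as a low-cost improvement. Both documents fix one baseline slope while allowing everything else of importance to vary by visit. The expected gain at Week 52 runs from nothing (flat slope) to about 3–7% of variance if the correlation falls from 0.6 to 0.3, and only a steeper fall or particular covariance patterns take it further. These figures rest on assumed correlations, constant SDs and complete data; a rising SD shrinks or removes the gain. The consequence is limited to the width of the visit-specific KCCQ-12 and EQ-5D intervals. Minor.

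**What to change.** Before unblinding, add `base*time` to the MODEL statement and a baseline-by-time term to the text of SAP 4.8.10, for each KCCQ-12 score and for the EQ-5D index. Keep LSMEANS at the mean baseline. Record the change in SAP section 5, since Protocol 12.10.3 lists the terms without it but leaves the detail to the SAP.

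The cost is 7 − 1 = 6 extra parameters for each KCCQ-12 model and 3 − 1 = 2 for EQ-5D, negligible with about 1,100 subjects. No new data are needed. Adding the term after unblinding would look data-driven.
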